# 7.5 Analysis of Safety

Safety analyses will be conducted using the safety population and summarized by treatment arms as treated.

Baseline laboratory results will be summarized using descriptive statistics by treatment arms. Worst toxicity grades per subject will be tabulated for selected AEs and laboratory analytes. Clinical safety data (including AEs, grade 3 and 4 hematologic and nonhematologic events, clinical laboratory evaluations, vital signs, ECGs and physical examinations) will be summarized by treatment groups using descriptive statistics or frequency distribution as appropriate.

Treatment-emergent period is defined as the duration of the study treatment plus 30 days. AEs occurring in this period are termed TEAEs.

Duration of treatment and total dose administered will be summarized by treatment groups. In addition, the number and percentage of subjects with dose reduction will be tabulated.

EudraCT number 2015-003869-28

- CONFIDENTIAL -

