## **1 INTRODUCTION**

A Statistical Analysis Plan (SAP) contains a more technical and detailed elaboration of the principal features of the analysis described in the protocol and includes detailed procedures for executing the statistical analysis of the primary and secondary endpoints and other data. This SAP contains details related to analyses specific to the Open Label Extension Period (OLE), in addition to the SAP (version 3.0) used for the primary analysis.

The SAP is finalized and signed prior to database hard lock to ensure lack of bias. If needed, revisions to the approved SAP may be made prior to database hard lock. Revisions will be version controlled.

This statistical analysis is coordinated by the responsible biostatistician of Astellas Pharma. Any changes from the analyses planned in the SAP will be justified in the Clinical Study Report.

Prior to database hard lock, a final blinded review of data and TLFs meeting will be held to allow a review of the clinical trial data and to verify the data that will be used for any new analysis set classification. If required, consequences for the statistical analysis will be discussed and documented. A meeting to determine analysis set classifications may also be held prior to database hard lock.

This SAP for the open-label extension is a supplement to the main study SAP which was completed prior to unblinding the study. The methods for the analysis of overall survival were established in the main study SAP. This SAP includes those methods and adds sensitivity and subgroup analyses for overall survival and an updated analysis for time to new antineoplastic. This SAP also describes the planned summaries for safety, disposition, and other data to incorporate the placebo patients who crossed over to open-label enzalutamide.

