## **3** STUDY OBJECTIVE(S) AND DESIGN

## 3.1 Study Objective(s)

Refer to the study protocol for a full list of study objectives.

Efficacy objective in the open label extension period is to determine the benefit of enzalutamide plus ADT as compared to placebo plus ADT as assessed by overall survival (OS). Additionally, time to new antineoplastic therapy will be summarized descriptively as supportive information in the evaluation of the overall survival endpoint.

Safety objective is to determine the safety of enzalutamide plus ADT as compared to placebo plus ADT.

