#### 6.3 Treatment Emergent Adverse Event (TEAE)

A TEAE is defined as an AE that occurs or worsen at any time during the treatment emergent period. The treatment emergent period is time interval encompassing the double-blind treatment emergent period and the OLE treatment emergent period.

The double-blind treatment emergent period is defined as the time interval from the first double-blind study drug intake up to 30 days after the date of the last dose of double-blind study drug, study discontinuation, the start of new antineoplastic therapy, or the first dose of OLE treatment, whichever occurs first.

If AE start date is the same date as the study start, then it will be considered as a TEAE if the box 'Onset after first dose of study' is ticked in the Electronic case report form(eCRF). If a patient experiences an event both during the pre-investigational period and during the investigational period, the event will be considered as TEAE only if it has worsened in severity (i.e. it is reported with a new start date).

The OLE treatment emergent period is defined as the time interval from the OLE study drug intake up to 30 days after the date of the last dose of OLE study drug, study discontinuation, or the start of new antineoplastic therapy, whichever occurs first.

AE with both a missing start and stop dates, and AEs with a missing start date but has a known stop date which is on or after the first dose of study drug will be considered treatment-emergent.

For each treatment group, the treatment emergent period is as follows;

- Enzalutamide group: from the first DBT study drug intake up to 30 days after the date of the last dose of study drug, study discontinuation, or the start of new antineoplastic therapy, whichever occurs first.
- Placebo group: from the first DBT study drug intake up to 30 days after the date of the last dose of placebo, start of open-label enzalutamide, study discontinuation, or the start of new antineoplastic therapy, whichever occurs first.
- Placebo crossover group: from the first OLE study drug intake up to 30 days after the date of the last dose of OLE study drug, study discontinuation, or the start of new antineoplastic therapy, whichever occurs first.

AEs will be coded to System Organ Class (SOC) and preferred term using MedDRA v23.0 and severity graded using National Cancer Institute's Common Terminology Criteria version 4.03 (NCI-CTCAE v4.03) for AEs.

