## 7.5 Analysis of Safety

All analysis of safety will be presented for Enzalutamide, Placebo and Placebo crossover group on the SAF, unless specified otherwise. All AEs will be listed.

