#### 7.5.2 Clinical Laboratory Evaluation

Laboratory assessment will be done for the following parameters:

Hematology	Biochemistry	Other	
Red blood cell count	Albumin	Testosterone	
White blood cell count	Alkaline phosphatase (ALP)	PSA	
White blood cell differential	Alanine aminotransferase (ALT)		
Hemoglobin	Aspartate aminotransferase (AST)		
Hematocrit	Blood urea nitrogen		
Platelet count	Calcium		
	Creatinine		
	Glucose		
	Phosphorus		
	Potassium		
	Sodium		
	Total bilirubin		
	Total protein		

Quantitative clinical laboratory variables (hematology, serum chemistry and testosterone), will be summarized using mean, standard deviation, minimum, maximum and median for Enzalutamide, Placebo and Placebo crossover group at each visit. Additionally, a within-patient change will be calculated as the post-baseline measurement minus the baseline

measurement and summarized in the same way. Baseline is defined as the last available measurement prior to the first dose (double-blind or open-label extension).

Based on the NCI-CTCAE grade of laboratory data, clinical laboratory evaluations will be summarized by grade and by visit, for their comparison to the upper limit. Shift analysis tables on the enzalutamide group will present the shift from baseline to each visit and to the highest grade among the post-baseline visits, by grade. The number and percentage of patients with an increase in grade will be summarized by visit.

Each laboratory result will also be classified as low (L), normal (N), or high (H) at each visit according to the laboratory supplied reference ranges.

Laboratory data will be displayed in listings, along with their NCI-CTCAE grade.

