#### 7.12.3 Visit Windows

Visit windows are allowed for certain visits per the schedule of assessments. Patient data will not be excluded from analyses due to the patient's failure to comply with the visit schedule.

For summary tables reporting results by visit, analyses of efficacy and safety variables will be performed according to the analysis visit windows described in the following Table 4.

In the case of multiple observations in the same analysis visit window, the observation which is closest to the target date will be used. If the observations have the same distance to the target visit day, the latest one will be used (using date, and time if available). Should there be two assessments documented at the same time due to the repetition of analysis of the same sample, the one reported as scheduled will be used.

Scheduled Visit	Analysis Visit*			
Week 1 (Day 1)	Baseline**			
Week 5 (Day 29)	Week 5			
Week 13 (Day 85)	Week 13			
For the next visits during the treatment period:				
Week X = Week (i*12+13), (i=1,2,3,) Week X target day = i*12*7 + 85, (i=1,2,3,) Week X (Wk X target day - 41 days; Wk X target day + 42 days)				
However, for the (last) visit during the treatment period, i.e. the last dose day of study drug is recorded, the upper boundary of the analysis visit window is 5 days after the last dose day, e.g.				
Week X = Week (i*12+13), (i=0,1,2,3,) Week X target day = i*12*7 + 85, (i=0,1,2,3,) Week X (Wk X target day - 41 days; last dose day + 5 days)				
last dose day + 30 days	30 Day Safety F-up (after last dose or prior to new therapy)			
	Scheduled Visit Week 1 (Day 1) Week 5 (Day 29) Week 13 (Day 85) visits during the treatment = Week (i*12+13), (i=1,2) get day = i*12*7 + 85, (i=1) t day - 41 days; Wk X tar the treatment period, i.e. recorded, visit visit window is 5 day Week (i*12+13), (i=0,1, et day = i*12*7 + 85, (i=0) get day - 41 days; last do last dose day + 30 days			

Table 4Analysis Visit Windows

Visit Day Interval	Scheduled Visit	Analysis Visit*		
Patients who end treatment before the data analysis cut-off date and have long-term (LT) follow-up				
visits,				
have visits every 12 weeks after last dose day:				
LT F-up $j = j*12$ weeks visit after last dose day, $(j=1,2,3,)$				
LT F-up j target day = $j*12*7 + last dose day, (j=1,2,3,)$				
LT F-up j ( $j*12*7 + last dose day - 41$ ; $j*12*7 + last dose day + 42$ )				

F-up: follow-up

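### SAP 7.5.2 limits the laboratory shift tables, including the shift to highest grade, to the Enzalutamide group, so beyond the liver thresholds Placebo and Placebo crossover have no worst-value laboratory summary

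*SAP*

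**What the plan says.** SAP 7.5 sets the default: "All analysis of safety will be presented for Enzalutamide, Placebo and Placebo crossover group on the SAF, unless specified otherwise". SAP 7.5.2 then narrows one output: "Shift analysis tables on the enzalutamide group will present the shift from baseline to each visit and to the highest grade", the highest grade being taken among the post-baseline visits. The neighbouring sentence on graded results, "clinical laboratory evaluations will be summarized by grade and by visit", names no group, nor does the sentence on increases in grade, so both fall under the default.

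SAP 6.3 treats crossover subjects as a group of their own, with their own period: "Placebo crossover group: from the first OLE study drug intake".

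The protocol is broader. Section 7.5 says "Worst toxicity grades per subject will be tabulated for selected AEs and laboratory analytes", within safety analyses summarized by arm as treated. Section 7.5.2 plans laboratory shift tables by CTCAE grade and reference range, with no limit to one arm.

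On purpose, SAP 3.1 states: "Safety objective is to determine the safety of enzalutamide plus ADT as compared to placebo plus ADT". SAP section 1 says the safety summaries are described in order "to incorporate the placebo patients who crossed over to open-label enzalutamide".

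**The concern.** A shift table to the highest grade answers a simple safety question: of the subjects who started at a given grade, how many reached grade 3 or 4 at any time on treatment? Where the objective is comparative, that count needs the same count on placebo beside it. Subjects who start enzalutamide after placebo are newly exposed, so their count has its own interest.

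As written, the table gives the count for one group only, and the SAP offers no reason. At stake is whether the extension report can state, outside the liver tests, how many Placebo and Placebo crossover subjects ever reached each laboratory grade.

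**Working it through.** No arithmetic decides this. The check is which groups each planned laboratory output covers, and whether it uses the worst value per subject.

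| Laboratory output | Source | Groups | Worst value per subject? |
|---|---|---|---|
| Values and change, by visit | SAP 7.5.2 | All three, named | No |
| Grade, by visit | SAP 7.5.2 | All three, by the 7.5 default | No |
| Increase in grade, by visit | SAP 7.5.2 | All three, by the 7.5 default | No |
| Shift to each visit | SAP 7.5.2 | Enzalutamide only | No |
| Shift to highest grade | SAP 7.5.2 | Enzalutamide only | Yes |
| Liver thresholds | SAP 7.5.2.1 | Each treatment group and total | Yes, in multiples of the upper limit of normal |
| Listing with grades | SAP 7.5.2 | Not restricted | Not a summary |

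1. **Worst CTCAE grade.** Only one table gives it, and that table is limited to Enzalutamide. The liver table gives worst values by group, but for liver tests only and not as CTCAE grades.

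2. **Whether by-visit tables can replace it.** Let n_j be the number of subjects in a group at grade 3 or 4 at visit j. From these counts alone, the number of subjects ever at grade 3 or 4 among the tabulated values is known only to lie between max(n_j) and the sum of the n_j, because the same subject may appear at several visits.

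3. **Which values enter the by-visit tables.** Where a window holds several observations, SAP 7.12.3 says "the observation which is closest to the target date will be used". For visits after Week 13 the window runs from 41 days before the target to 42 days after it, which is 41 + 1 + 42 = 84 days (12 weeks). The schedules of assessments allow clinical laboratory tests at unscheduled visits. A worse value further from the target than another value in the same window is therefore absent from the by-visit summaries. The last on-treatment visit has a different upper limit, and the Week 5 and Week 13 intervals are not legible in the text available, so the 84-day width is not claimed for those.

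4. **Whether the restriction fits the rest of the SAP.** Two other summaries based on each patient's highest value, the liver thresholds (7.5.2.1) and blood pressure (7.5.3), are not confined to one group. The laboratory shift table is the exception.

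**The case against.** The strongest objection is that the gap is smaller than the sentence in 7.5.2 suggests, and may be partly filled elsewhere.

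- **Main study SAP.** This SAP supplements a main study SAP that is not among the documents. Shift tables for double-blind placebo may be there. This stands for Placebo. It helps less for crossover: SAP section 1 says the main SAP was completed before unblinding, Protocol 12.6.1 places open-label treatment after unblinding, and the supplement took on the crossover summaries.
- **Meaning of the enzalutamide group.** Protocol 12.6.7 plans a combined summary of everyone who received enzalutamide, and SAP 7.2.1 uses a similar label for open-label disposition. The shift table might be meant to pool crossover subjects. SAP 6.3 and 7.5 list them separately, so exclusion is the likelier reading. Even if pooled, Placebo would still have no table.
- **Protocol wording.** Protocol 7.5 speaks of selected analytes without naming them, and the liver table arguably meets part of that.

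A reader might also infer that laboratory toxicity has no comparator at all, that neutropenia cannot be set against placebo, or that off-target values are lost. The documents do not support these readings. Worst liver values are compared by group, and grade-by-visit tables cover all three groups. Neutropenia as an event of special interest is defined by adverse event terms and reported per treatment group, as are events of grade 3 or higher. All laboratory values are listed with their grades. What remains is that Protocol 5.5.1 makes a laboratory abnormality an adverse event only when it meets stated criteria, one of which is investigator judgment, so adverse event tables only partly replace graded laboratory data.

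Nor can one assume that the highest-grade column already captures every value. SAP 7.5.2 refers to post-baseline visits and does not say whether unscheduled results count.

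**Conclusion.** The point holds as a scope discrepancy in a descriptive safety table. By its own wording, SAP 7.5.2 overrides the three-group default and is narrower than Protocol 7.5 and 7.5.2. Two of three reporting groups have no worst-post-baseline laboratory summary in this SAP other than the liver thresholds.

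The number of subjects affected cannot be given. The protocol plans about 550 randomized subjects per arm, but that is neither the safety population nor the number who crossed over, and the documents give no crossover count.

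The conclusion assumes that the enzalutamide group in 7.5.2 means the group defined in SAP 6.3, and it is limited to this SAP. It would weaken for Placebo if the main study SAP already specifies that table. The overall survival test is unaffected. The change is still worth making, because the safety objective is comparative and the data are already collected and graded.

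**What to change.** In SAP 7.5.2, reword the sentence so that the shift tables are produced for the Enzalutamide, Placebo and Placebo crossover groups. Add that:

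- each group is measured from its own baseline as defined in 7.5.2 and 7.12, which for Placebo crossover is the last value before open-label enzalutamide;
- each group is restricted to its own treatment-emergent period in 6.3;
- the highest-grade column uses all post-baseline values, scheduled and unscheduled;
- duration of exposure by group is shown beside the counts.

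If the restriction is intended, state the reason and point to where the Placebo and Placebo crossover results are reported.

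The cost is two more groups in a planned table, with no new data collection. There is a downside in interpretation. The chance of ever reaching a grade rises with time observed. In 6.3 the Placebo period ends no later than the start of open-label enzalutamide, while the Enzalutamide period can run through both study periods, and SAP 7.3.1 tabulates exposure out to 4 years. Raw worst-grade proportions would therefore tend to look less favourable for the group observed longer, and must be read with exposure.

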#### 7.5.2.1 Liver Enzymes and Total Bilirubin

The following potentially clinically significant criteria for liver tests - ALP, ALT, total bilirubin, AST, and their combination - are defined. The patient's highest value during the investigational period will be used.

Parameter	Criteria (Upper limit of normal[ULN])
ALT or AST	> 3xULN
	> 5xULN
	> 8xULN
Total Bilirubin	> 2xULN
ALT and/or AST AND Total Bilirubin (*)	(ALT and/or AST > 3xULN) and total bilirubin > 2xULN
ALT and/or AST AND Total Bilirubin (*) AND Alkaline phosphatase	(ALT and/or AST > 3xULN) and total bilirubin > 2xULN and Alk phos <2x ULN

(\*) Combination of values measured within same sample

The number and percentage of patients with potentially clinically significant values in liver enzyme and total bilirubin tests during the investigational period will be presented by treatment group and overall.

#### 7.5.3 Vital Signs

Vital signs (systolic blood pressure, diastolic blood pressure, and pulse rate) will be summarized using mean, standard deviation, minimum, maximum and median for Enzalutamide, Placebo and Placebo crossover group at each visit. Additionally, a withinpatient change will be calculated per visit as the post-baseline measurement minus the baseline measurement and summarized in the same way. Baseline is defined as the last available measurement prior to the first dose (double-blind or open-label extension).

Finally based on the patient's highest value during the treatment period, a summary will present the number and percentage of patients with blood pressure elevation (systolic:  $\geq 140 \text{ mmHg}, \geq 180 \text{ mmHg}$ ; diastolic:  $\geq 90 \text{ mmHg}, \geq 105 \text{ mmHg}$ ), with increase from

baseline (systolic:  $\geq 10 \text{ mmHg}$ ,  $\geq 20 \text{ mmHg}$ ; diastolic:  $\geq 5 \text{ mmHg}$ ,  $\geq 15 \text{ mmHg}$ ) or combination criteria (systolic:  $\geq 140 \text{ mmHg} \& \geq 20 \text{ mmHg}$  increase from baseline,  $\geq 180 \text{ mmHg} \& \geq 20 \text{ mmHg}$  increase from baseline; diastolic:  $\geq 90 \text{ mmHg} \& \geq 15 \text{ mmHg}$ increase from baseline,  $\geq 105 \text{ mmHg} \& \geq 15 \text{ mmHg}$  increase from baseline) or any of these criteria.

All vital signs results will be provided in a listing.

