Lastly, the primary efficacy analysis in ARCHES demonstrated a statistically significant, robust and substantial improvement in radiographic progression-free survival together with clinically meaningful improvements in the key secondary endpoints of time to PSA progression, time to start of a new antineoplastic therapy, PSA undetectable rate and objective response rate and a trend in OS (observed at the time of interim analysis) in favor of enzalutamide plus ADT versus placebo plus ADT treatment. For the secondary endpoints, the ARCHES study demonstrated that enzalutamide prolonged the time to the first symptomatic skeletal event and time to castration-resistance. Assessments of patient-reported outcomes data showed that patients receiving enzalutamide plus ADT in ARCHES had a high baseline level of quality of life, which was maintained over time.

Based on the safety information collected to date in clinical trials and in commercial use, the safety profile experienced by patients remains consistent with the approved product label as well as events that can be seen in patients with prostate cancer. The safety profile in mHSPC patients in this study is expected to be consistent with the established safety profile for enzalutamide. To date, there are 4 important identified risks associated with enzalutamide (seizure, fall, nonpathological fracture and ischemic heart disease). While serious adverse events (SAEs) such as seizure have occurred in patients receiving treatment with enzalutamide, these events have been rare. To mitigate the risk of seizure, subjects with a history of seizure or any condition that may predispose to seizure (e.g., prior cortical stroke or significant brain trauma, brain arteriovenous malformation) are excluded from the trial. Study drug discontinuation is required for subjects experiencing either seizure or PRES. In addition to these patient exclusion and discontinuation requirements, the study design includes safety labs, scans and guidance related to concomitant medications to minimize the risks associated with enzalutamide and ensure timely intervention if needed.

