# 5.4 Safety Assessment

#### 5.4.1 Vital Signs

Routine vital signs, including blood pressure, pulse and temperature will be assessed at the screening visit, at every clinic visit while on study drug and at the safety follow-up visit.

EudraCT number 2015-003869-28

- CONFIDENTIAL -

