# 7.1 Sample Size

As originally planned, approximately 1100 subjects (550 subjects per treatment arm) will be randomized in the study.

The final analysis of rPFS will be conducted with a minimum of 262 progression events based on the following considerations:

- A target HR is 0.67. The expected median rPFS for the ADT arm is 20 months as measured from the date of randomization. A target HR of 0.67 corresponds to approximately 50% increase in median rPFS for the enzalutamide plus ADT arm relative to the placebo plus ADT arm (approximately 30 versus 20 months).
- The required minimum of 262 rPFS events (radiographic progression or death on study, defined as death from any cause within 24 weeks after treatment discontinuation, whichever occurs first) provides 90% power to detect a target HR of 0.67 based on a 2-sided log-rank test and significance level of 0.05.

Additionally the study is powered for OS. Specifically, 342 death events will be required to provide 80% power to detect a target hazard ration of 0.73 with a target difference in Kaplan-Meier estimated median of approximately 15 months (40 months for placebo versus 55 months for enzalutamide) at the 4% significance level. This significance level was chosen to apply a parallel testing strategy between OS and some other secondary endpoints (with allocated type I error rate of 1%) as described in Section 7.4.2.

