#### 2 FLOW CHART AND VISIT SCHEDULE

### 2.1 Double blind Period

#### 2.2 **Open Label Extension**

\*Week 5 visit required only for subjects who received placebo + ADT during the double-blind period

Study Day	Screening Visit	1	29	85 and Every Subsequent 84 Days	Safety Follow-up	Unscheduled	Long Term Follow-up‡
Study Week	-4 to -1 (28 Days)	1	5	13 and Every Subsequent 12 Weeks	30 Days after Last Dose§	Visit†	Every 12 Weeks
Window (Days)			± 5	± 5	± 7	NA	± 7
Informed Consent	Х						
Medical History	Х						
Inclusion/Exclusion Criteria	Х	Х					
Randomization (IRT)		Х					
Vital Signs	Х	Х	Х	Х	Х	Х	
Physical Examination including Weight	Х	Х	Х	Х	Х	Х	
Height	Х						
12-lead Electrocardiogram	Х	Х			Х		
Clinical Labs ††	Х	Х	Х	Х	Х	Х	
Prostate-specific antigen	Х	Х	Х	Х	Х		
Sample for Genotyping Analysis ‡‡		Х					
CCI		Х		Х			
Testosterone				Х			
CT/MRI and Bone Scan§§, ¶¶	X§§			X¶¶			Х
Chest X-ray or Chest CT/MRI †††	Х			Х			Х
ECOG Performance Status	Х	Х	Х	Х	Х	Х	
QoL Assessment (QLQ-PR25, EQ-5D-5L, FACT-P,		v		v	v		$\mathbf{V}^{\mathbf{+}}$
BPI-SF)		Л		Λ	Λ		Λ.
Adverse Events§§§	Х	Х	Х	X	Х	Х	
Previous and Concomitant Medications	Х	Х	Х	X	Х	Х	
Study Drug Dispensing		Х	Х	X			
Study Drug Treatment		Х	Х	Х			

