## 3.2 Study Design

This is a multinational phase 3, randomized, double-blind, placebo-controlled efficacy and safety study of enzalutamide plus ADT versus placebo plus ADT in patients with mHSPC. After the double-blind period has completed, eligible patients were allowed to received open label enzalutamide in an open label extension period.

Approximately 1100 subjects were randomized centrally 1:1, and the randomization was stratified by volume of disease (low versus high) and prior docetaxel therapy for prostate cancer (no prior docetaxel, 1-5 cycles, 6 cycles). High volume of disease is defined as metastases involving the viscera or, in the absence of visceral lesions, there must be 4 or more bone lesions, at least 1 of which must be in a bony structure beyond the vertebral column and pelvic bone. Prior docetaxel therapy is defined as 1 or more cycles of docetaxel but no more than 6 cycles.

In this study, patients received 4 capsules of enzalutamide (40 mg each) or placebo per day orally in the double-blind period. After the double-blind period has completed, eligible patients received 4 capsules of enzalutamide (40 mg each) in the open label extension period. As long as the patient is tolerating the study drug, the treatment should be continued until radiographic disease progression (rPD) or starting an investigational agent or new therapy for treatment of prostate cancer. Patients who discontinue study drug without radiographic progression will continue to follow the radiographic assessment schedule until radiographic progression event or until the target number of deaths is reached for the final analysis of OS.

The following assessments of prostate cancer status will be collected during OLE: soft tissue disease on CT scan or on MRI, bone disease on radionuclide bone scans, survival status, EQ-5D-5L, QLQ-PR25, FACT-P for QoL and BPI-SF for pain symptom assessment. Throughout the study, safety and tolerability were assessed by the recording of adverse events (AE), vital signs, physical examinations, 12-lead electrocardiograms (ECG), and safety laboratory evaluations (including PSA).

Patients will have a safety follow-up visit 30 days after their last dose of study drug or prior to initiation of new antineoplastic therapy for prostate cancer, whichever occurs first. All

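### The blood-pressure threshold table uses each patient's highest reading over unequal treatment periods, so it is expected to show more elevations on enzalutamide even with no drug effect

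*SAP*

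**What the plan says.** SAP 7.5.3 applies its blood-pressure rows (absolute level, rise from baseline, and both together) to one number per patient: "based on the patient's highest value during the treatment period, a summary will present the number and percentage of patients with blood pressure elevation". It does not define the treatment period for this table, and it gives no common window, censoring rule or exposure adjustment.

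Four other provisions determine how many readings enter that maximum.

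- **When pressure is read.** Protocol 5.4.1 has vital signs taken "at every clinic visit while on study drug and at the safety follow-up visit". In the schedule of assessments (SAP section 2, Table 1), post-baseline visits fall at week 5 and then at week "13 and Every Subsequent 12 Weeks".
- **How long treatment lasts.** Under SAP 3.2, "the treatment should be continued until radiographic disease progression (rPD) or starting an investigational agent or new therapy".
- **What is expected and known about progression.** Protocol 7.1 plans median rPFS at "approximately 30 versus 20 months". Protocol 1.4 reports that "the primary efficacy analysis in ARCHES demonstrated a statistically significant, robust and substantial improvement in radiographic progression-free survival".
- **Group periods.** The only group-specific periods are the adverse-event ones in SAP 6.3. One reads "Enzalutamide group: from the first DBT study drug intake up to 30 days after the date of the last dose of study drug", which includes the extension. The other reads "Placebo group: from the first DBT study drug intake up to 30 days after the date of the last dose of placebo, start of open-label", which closes it at crossover.

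**The concern.** The maximum of several variable readings tends to rise with the number of readings. If enzalutamide patients stay on drug longer, each has more chances to cross a threshold once. The percentages then differ between arms before any pharmacological effect is considered. Placing every reading in the correct column does not remove this. Cutting Placebo at open-label start, which is right for attribution, widens the gap in the number of readings.

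Hypertension is an adverse event of special interest (SAP Table 3). In this SAP, section 7.5.3 is the only place where measured blood pressures are counted against thresholds. A reader of the report would naturally compare the two columns and take the gap as a drug effect.

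**Working it through.** The plan states no expected percentage for this table, so there is no figure to reproduce. The planning medians agree with each other: 20 / 0.67 = 29.9 months, which the Protocol rounds to 30.

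**Step 1: readings implied by the schedule.** A month is 30.4375 days (SAP 7.12) and visits fall at weeks 5, 13, 25 and so on.

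- 20 months = 87.0 weeks: last visit week 85, 8 readings.
- 30 months = 130.4 weeks: last visit week 121, 11 readings.
- 48 months = 208.7 weeks: last visit week 205, 18 readings.

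**Step 2: why the count matters.** Let a patient's true level be θ and let visit errors be independent normal with SD σ. With k readings,

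P(max ≥ c) = 1 − E[Φ((c − θ)/σ)^k]

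P(max − baseline ≥ 20) = 1 − ∫ φ(z) Φ(20/σ + z)^k dz

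Both increase with k whenever σ > 0. With σ = 12, the rise ≥ 20 row is 41.5% for 8 readings and 46.9% for 11.

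**Step 3: staggered time on drug.** Patients stop at different times, so fixed counts overstate the contrast. Assumptions, none of them in the documents:

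- Systolic mean 132 and between-patient SD 12 mmHg, the same in both arms (no drug effect).
- Within-patient SD 10 or 12 mmHg.
- Exponential time on drug with medians 20 and 30 months, using planned rPFS as a proxy.
- Administrative cuts as shown.

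There are 300,000 simulated patients per arm in each row. Percentages are of patients with at least one post-baseline reading, following the non-missing denominator rule in SAP 7.12. Each cell is Placebo versus Enzalutamide, in percent.

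| Cut, months (P / E) | Mean readings | Within SD | ≥140 | Rise ≥20 | Both | ≥180 |
|---|---|---|---|---|---|---|
| 24 / 24 | 6.5 v 7.2 | 10 | 61.3 v 63.5 (+2.2) | 26.5 v 28.0 (+1.5) | 20.1 v 21.5 (+1.4) | 0.5 v 0.6 |
| 24 / 24 | 6.5 v 7.2 | 12 | 66.5 v 69.3 (+2.8) | 35.8 v 38.1 (+2.3) | 28.7 v 30.9 (+2.2) | 1.3 v 1.4 |
| 30 / 48 | 7.3 v 11.3 | 10 | 62.4 v 67.7 (+5.3) | 27.7 v 33.1 (+5.4) | 21.3 v 26.4 (+5.1) | 0.6 v 0.8 |
| 30 / 48 | 7.3 v 11.3 | 12 | 67.7 v 73.6 (+5.9) | 37.1 v 43.4 (+6.3) | 30.1 v 36.6 (+6.5) | 1.4 v 1.9 |
| 18 / 42 | 5.5 v 10.6 | 10 | 59.3 v 67.2 (+7.9) | 24.4 v 32.2 (+7.8) | 18.2 v 25.6 (+7.4) | 0.5 v 0.8 |
| 18 / 42 | 5.5 v 10.5 | 12 | 64.6 v 73.0 (+8.4) | 33.5 v 42.7 (+9.2) | 26.4 v 35.8 (+9.4) | 1.1 v 1.8 |

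The common cut corresponds to reading the treatment period as the double-blind period only. The unequal cuts correspond to the SAP 6.3 periods.

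**Step 4: candidate repairs under the same null** (cuts 30 / 48, within-patient SD 10).

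- Kaplan-Meier proportion with a first rise ≥ 20: 24.3% v 24.2% at week 49 and 32.7% v 32.6% at week 97. For a first reading ≥ 140 at week 97: 69.5% v 69.5%. The artefact disappears.
- Highest value through week 49 only: 55.9% v 57.2% at ≥ 140 and 21.5% v 22.2% for rise ≥ 20. Across both SDs and the three rows, 0.5 to 1.6 points remain, because early discontinuers have fewer readings.
- Crude first-exceedance rate per 100 patient-years at ≥ 140: 82.5 v 68.0. The bias reverses, because the hazard of a first exceedance falls with time.

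**The case against.** The strongest reply is that little depends on this table. It is descriptive: Protocol 7.5 plans only descriptive summaries of vital signs, and SAP 7.5.3 names no test. The same section gives mean, median and within-patient change at every visit for all three groups, and per-visit summaries do not carry the maximum-of-many problem. SAP 7.5.1 adds adverse-event rates per 100 patient-years, plus interval tables for the commoner events with patients still on treatment as denominator. Hypertension as an event of special interest is identified from coded terms, not from this table. All of this stands. It limits the harm, but it does not correct the threshold percentages, because none of these summaries counts how many men crossed a given measured pressure over comparable follow-up.

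The size also rests on assumptions. Planned median rPFS is not time on drug: Protocol 6.1 ties stopping at progression to the investigator's judgment about benefit, and patients stop for other reasons. Readings at unscheduled visits are left out of the count. The main SAP (version 3.0) is not available here, so whether it has a double-blind threshold table cannot be checked.

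A reader might infer three stronger things that the documents do not support.

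- **That a true effect can no longer be told from the artefact.** The per-visit and exposure-adjusted summaries contradict that. The Protocol's pooled hypertension rates per 100 patient-years (8.2 versus 5.5, section 1.3) also make a real effect plausible.
- **That the false excess is about 12 points and would be highly significant.** That figure needs 7 versus 14 readings for every patient (39.2% versus 51.1% for rise ≥ 20, SD 12). No section implies that contrast, and no test is planned.
- **That every row is materially affected.** The ≥ 180 row is almost unchanged.

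The direction is against enzalutamide, so the table overstates harm and does not conceal it. That lowers the urgency but does not make the comparison valid.

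**Conclusion.** The point holds as an expected bias in one descriptive table. Followed as written, SAP 7.5.3 is expected to show more blood-pressure elevations on enzalutamide with no effect on blood pressure.

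The direction needs only visit-to-visit variation and longer exposure on enzalutamide. The design leads to longer exposure even under a common cut, and more so if the SAP 6.3 periods apply.

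The size is conditional on the assumed blood-pressure distribution and time on drug. For the ≥ 140, rise ≥ 20 and combined rows it is about 2 to 3 points with a common 24-month cut (1.4 to 2.8 in the runs) and about 5 to 10 with longer enzalutamide follow-up (5.1 to 9.4). It is under 1 point at ≥ 180. Diastolic rows were not simulated but follow the same rule. This is an expectation, not a certainty in one sample, and it does not show that enzalutamide lacks a blood-pressure effect.

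**What to change.** In SAP 7.5.3:

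1. State the period that this table covers for each group.
2. For Enzalutamide versus Placebo, report the Kaplan-Meier proportion with a first exceedance of each threshold at fixed weeks. Censor each patient at the end of his group's treatment window, with Placebo censored at the start of open-label enzalutamide.
3. If wanted, add the highest value over a common double-blind window as a supplement, noting that early discontinuers still have fewer readings.
4. Do not use a crude rate per patient-year for first exceedances.
5. Keep the whole-period maximum as a within-group figure, with a footnote that it is not comparable between groups of different exposure.

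The liver-test table in SAP 7.5.2.1 also uses the highest value, so the same footnote would suit it.

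The cost is some SAP wording and one extra table from data already collected. Late exceedances carry less weight in the between-arm comparison, and Kaplan-Meier assumes that censoring at treatment end is non-informative, which should be stated.
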